DSM-V	Diagnostic and Statistical Manual of Mental Disorders, Fifth Edition
FDA	U.S. Food and Drug Administration
FTND	Fagerstrom Test of Nicotine Dependence
GABA	Gamma-Aminobutyric Acid
GAD-7	General Anxiety Disorder-7
GBDP	Global Burden of Disease Project
HCG	Human Chorionic Gonadotropin
ICF	Informed Consent Form
MAR	Missing At Random
MINI	Mini International Neuropsychiatric Interview
MNSW	Minnesota Nicotine Withdrawal Scale
NIBS	Non-Invasive Brain Stimulation
PHQ-9	Patient Health Questionnaire-9
REB	Research Ethics Board
REDCap	Research Electronic Data Capture
RMT	Resting Motor Threshold

RPN	Research Practice Nurse
rTMS	Repetitive Transcranial Magnetic Stimulation
TASS	TMS Adult Safety Screening Questionnaire
TLFB	Timeline Follow-Back
TMS	Transcranial Magnetic Stimulation
TCQ-SF	Tobacco Craving Questionnaire-Short-Form
TTC	Toronto Transit Commission

CLINICAL TRIAL SUMMARY

Title	Accelerated deep transcranial magnetic stimulation for smoking cessation
Short Title	adTMS smoking
Phase	Phase II
Methodology	One-arm, open-label pilot study
Clinical trial Duration	24 months
Participating site(s)	2 sites: Waypoint Centre for Mental Health Care and Sunnybrook Research Institute
Objectives	To examine the efficacy of accelerated deep transcranial magnetic stimulation on smoking abstinence
Number of Participants	40, aiming 30 completers
Duration of Intervention	5 days
Statistical Methodology	Descriptive statistics, mixed effect logistic regression, and linear/generalized mixed models will analyze abstinence and secondary outcomes, adjusting for covariates and missing data under the MAR assumption

1.0 INTRODUCTION

Tobacco use disorder is a serious and growing public health issue. The Global Burden of Disease Project (GBDP) estimated that 1.14 billion people smoked worldwide in 2019[1]. Smoking tobacco accounts for 7.69 million deaths per year and is the leading risk factor for death among males[1]. Increasing therapeutic strategies effective for the treatment of tobacco use disorder is therefore of tremendous importance. While first-line pharmacotherapies for tobacco use disorder demonstrate efficacy for short-term smoking cessation, relapse remains a challenge for smokers[2,3]; more modalities to address smoking cessation are needed.

In recent years, non-invasive brain stimulation (NIBS) approaches, such as transcranial magnetic stimulation (TMS), have gained attention. In 2020, the U.S. Food and Drug Administration (FDA) approved a deep TMS system for use in smoking cessation in adults[4], which was also approved by Health Canada in 2022, marking the first approval in the addiction field. This system focuses on the insula, which has been recognized as being related to nicotine cues and the self-administration of nicotine[5,6] in our previous studies. Our group has also evaluated deep TMS's efficacy in smoking cessation as an add-on treatment strategy to varenicline[7]. Beyond addiction, TMS has been approved and utilized in many neuropsychiatric disorders, such as treatment-resistant depression and obsessive-compulsive disorder, and has gradually developed many different modalities within TMS. One of these promising modalities is the accelerated protocol for TMS (aTMS).

aTMS could reduce depressive symptoms with a large effect size[8], which is comparable to or even superior to the standard TMS protocol in some settings[9,10]. For depression, deep aTMS could reach response and remission in less than one week, with such effects persisting for up to 6 months[11]. Given the great potential of this TMS protocol and the current need to expand and improve the modality for smoking cessation, we aim to examine deep aTMS's efficacy in smoking cessation and relapse prevention. To our knowledge, this will be the first trial testing deep aTMS for tobacco use disorder.

1.1 Background

Disease burden of smoking: The Global Burden of Disease Project (GBDP) estimated that the number of smokers worldwide increased from under 1 billion in 1990 to 1.14 billion in 2019[1,12]. Smoking is more prevalent among individuals with mental health disorders and co-addictions, such as substance use disorder, anxiety, depression, phobias, psychosis, and antisocial personality or conduct disorders[13–16]. Smoking that begins in adolescence or young adulthood and continues throughout life has a more severe impact on health than smoking that starts later or is not persistent[17,18]. If current trends continue, at least 320 million smoking-related deaths will occur among those under 30 unless they quit[19]. The mortality rate among long-term smokers could

be greater than one in two, potentially reaching as high as two in three[17, 18, 20, 21], with half of these deaths likely occurring in middle age (30-69 years), leading to a loss of two or more decades of life[17, 18]. Smoking remains the leading cause of premature death before age 70 in much of Europe and North America[17, 18]. However, smoking cessation significantly reduces the risks associated with smoking. Smokers who quit before age 40 can avoid nearly all the increased mortality risks[19, 21], and those who quit by age 50 reduce their risk of death from lung cancer by about two-thirds[22]. Given the significant health risks and high mortality associated with smoking, particularly among vulnerable populations, investigating new modalities for smoking cessation is crucial to reducing these risks and improving public health outcomes.

Repeated Transcranial Magnetic Stimulation (rTMS) as an innovative approach: rTMS is a technique that has been found to be useful as a potential treatment for neuropsychiatric diseases. rTMS is non-invasive, does not require anesthesia, and is not associated with significant side effects. There is compelling evidence that rTMS works by affecting the function of neuronal circuits and inducing local changes in neural excitability. Transient inactivation of a specific brain structure can also be induced in humans through rTMS, through mechanisms that are likely associated with potentiation of GABAB receptor mediated inhibitory neurotransmission[23]. However, rTMS effects are complex and likely involve local modifications in the dynamic release patterns of various neurotransmitters, including dopamine[24–28]. The fact that there is in vivo evidence that rTMS of frontal brain regions has a modulatory effect on dopaminergic system, suggest that rTMS may be particularly useful in neuropsychiatric disorders associated with dopamine dysfunction, such as addiction[25, 29]. Moreover, with the recent development of Deep rTMS H-coils, it has become feasible to perform rTMS on deeper brain structures such as the insula[30–32].

Insula as a target structure: Several lines of research implicate the insula as a critical substrate in nicotine dependence following evidence that insular lesions produce a loss of self-reported cravings for cigarettes and immediate cessation of smoking without relapse[33, 34]. As observed and examined by Naqvi et al., smokers with brain damage involving the insula are more likely to experience a disruption in their smoking addiction, often resulting in the ability to quit smoking without relapse and persistent urges, compared to smokers with brain damage that does not involve the insula[34]. They further proposed that the insula plays a role in the recall of the interoceptive effects of drug taking, and through interactions with other brain regions, mediates conscious urges and decision-making precipitating relapse[35]. This hypothesis is supported by preclinical studies[5, 6, 36–38] conducted at our translational addiction research laboratory, where we demonstrated that electrical stimulation at insular cortex significantly reduced nicotine-taking and nicotine-seeking behaviors triggered by cues and priming. These effects appear to be specific to nicotine-related behaviors, as stimulation did not affect food-taking behavior[6]. Additionally, GABA agonist-induced inactivation of both the granular and agranular insular cortex reduced nicotine self-administration[5, 36]. Our previous preclinical studies have also shown that the insula plays a pivotal role in other addictions, including alcohol intake behavior[37] and rodent gambling task[38]. Neuroimaging studies further evidence significant associations

between cue-induced activation of the insula and self-reported craving for a cigarette[39], with greater bilateral insular pre-quit activity also predicting relapse in smokers[40]. Alongside the approval of deep TMS for clinical use in smoking[41], our laboratory has also tested the utility of insula-targeting deep TMS as an adjunctive treatment to varenicline, a psychopharmacological agent used for smoking cessation[7].

1.2 Study Intervention

Accelerated Transcranial Magnetic Stimulation (aTMS) protocols are increasingly being explored to address the practical challenges of conventional repetitive TMS (rTMS) and to enhance overall efficacy. Conventional rTMS typically involves one session daily over several weeks. In contrast, aTMS intensifies this approach by delivering multiple sessions per day, ranging from 2 to 10 sessions. In this study, we will implement the H4 deep aTMS protocol, administering 20 sessions over one week—four sessions daily for five consecutive days—targeting the bilateral insular cortex and prefrontal cortex using the Health Canada-approved H4 coil. The parameters used in each session will adhere to those approved by Health Canada, and will be described later (see Section 5.1). This method aims to improve efficacy and accessibility for smoking cessation, building on a more condensed and intensive schedule.

1.3 Preclinical Data to Date

Our Translational Addiction Research Laboratory has collected significant pre-clinical evidence supporting this trial. Preclinical results from our studies reveal that temporary insular inactivation in rats leads to reduced nicotine self-administration and seeking after exposure to nicotine-associated cues or a priming dose (Figure 1)[5,6]. These findings have been replicated under several conditions in rodent models, demonstrating that silencing the granular or agranular subregions of the insular cortex via local infusions of GABA receptor agonists (baclofen and muscimol) decreases both the motivation to self-administer nicotine and the likelihood of relapse when nicotine cues or priming doses are reintroduced [5,6,37].

Mechanistically, these results suggest that the insula integrates the interoceptive and affective states that drive nicotine use—disrupting insular activity weakens the craving and “urge” signals that typically reinforce smoking behavior [5,37]. Notably, such insular manipulations have been shown to have minimal effects on other reinforcers, such as food, indicating a degree of specificity for nicotine dependence[5]. Overall, these insights underscore the critical role of the insula in the neurocircuitry of tobacco addiction and support targeting insular function as a promising approach for reducing nicotine use and preventing relapse in smokers.

[figure not shown]

Figure 1. Effect of insula inactivation on (A) nicotine- (.15 mg/kg SC, 10 min before the session) or (B) cue-induced reinstatement of nicotine seeking tests after extinction (n = 8 and n = 6, respectively).; **p<0.01; ***p<0.001. Extracted from [5].

1.4 Clinical Data to Date

In a clinical trial, our group has suggested the efficacy of deep TMS in smoking cessation as an add-on treatment strategy to varenicline (Figure 2)[7].

[figure not shown]

Figure 2. Abstinence rates at Week 4, 12, and 26. Abstinence was measured by 7- day point-prevalence abstinence. All measures were confirmed with plasma cotinine. Bars represent (±) standard error. Group sample sizes: Week 4 (n =18 active, n =16 sham), Week 12 (n =17 active, n =15 sham), and Week 26 (n = 16 active, n =15 sham).; *p<0.05.

In previous aTMS depression studies, the effect of aTMS may be attributed to several factors, including optimized neurocircuit-based targeting, an accelerated treatment schedule, and a higher total pulse count[42–46]. Optimized neurocircuit-based targeting can be achieved through e-field modeling or personalized, connectivity-based biomarkers, such as DLPFC-subgenual anterior cingulate cortex connectivity[42]. The higher total pulse count may also contribute to positive treatment outcomes. For example[47], 90,000 pulses delivered with accelerated protocol (1,800 pulses per session, 10 sessions per day, 5 days per week, over one week) demonstrated better efficacy in treating depression compared to 18,000 pulses administered through a standard protocol (600 pulses per session, 1 session per day, 5 days per week, over 6 weeks). However, the individual components of aTMS still need to be isolated. Many

previous aTMS depression studies combine more than one of these factors. Therefore, even when considering aTMS beyond smoking cessation, isolating the effect of the accelerated treatment schedule is crucial to understand this technique.

1.5 Risks/Benefits

Risk: Several recent investigations have demonstrated that aTMS maintains a favorable safety profile similar to conventional once-daily protocols[47–49]. In a real-world study of accelerated deep TMS for major depression, no serious adverse events were observed among 111 patients receiving two to ten sessions per day[11]. Parallel evidence from a transdiagnostic review of 63 aTMS studies likewise concluded that aTMS appears to be safe and well-tolerated, with adverse event rates comparable to once-daily TMS[50].

The most serious potential adverse event with TMS is seizure. Among 1543 participants undergoing 43,873 aTMS sessions, only one seizure (0.0023%) was reported—a rate similar to or lower than that of conventional rTMS delivered once per day[50]. Notably, the patient who experienced this single event later resumed standard once-daily TMS safely and achieved remission.

Headaches are the most frequently reported side effect, and aTMS is no exception, though rates appear comparable to those in conventional once-daily rTMS. In the aTMS review, 28.4% of participants reported headaches, followed by mild, transient scalp pain or discomfort (8.3%)[50]. Similar to once-daily TMS, these effects often diminish over the first few sessions. Apart from headache and scalp discomfort, side effects such as fatigue and other adverse events remained below 10%, and dropout rates attributable to side effects were approximately 2%[50].

This underscores that intensifying the treatment schedule with multiple daily sessions does not substantially amplify risk. Overall, the safety and tolerability of aTMS are consistent with the well-established profiles observed in standard TMS protocols.

Benefit: The advantage of an accelerated approach is based on three theoretical reasons[9,51]. First, it presumes that equal or greater effects can be achieved by repeatedly applying stimulation within a short time interval. Second, it suggests that the effects induced within densely scheduled sessions have durable efficacy. Third, aTMS has the theoretical advantage of an accelerated response to treatment, given that it clusters the stimulation intervention within days. Regarding the theoretical equal or greater effect of aTMS, neurophysiologic evidence supports this by showing that a greater effect on cortical excitability is observed if a second rTMS session is administered within 24 hours of the first session[52]. Such equal or greater effects are also observed clinically in patients with depression treated with aTMS[9]. The durability

and rapid onset of the proposed effects have also been demonstrated in naturalistic studies applying aTMS for depression[11]. Supporting a more densely clustered protocol, other research has proposed a dose-response relationship for rTMS, indicating that the number of stimuli and total session number correlate with the response[53].

In addition to the possible benefits already mentioned, examining the efficacy of aTMS for smokers has practical significance. The daily administration of rTMS over several weeks can limit its accessibility, particularly for patients who are working or must travel long distances to reach a treatment site[54]. Furthermore, individuals with tobacco use disorder often struggle with treatment adherence, even with psychopharmacological approaches[55], while longer treatment courses are more difficult to adhere to. About 98% of adults with tobacco use disorder complete psychopharmacological treatment in randomized controlled trial[56], but only 25~30% of adults with tobacco use disorder complete nicotine replacement therapy or psychopharmacological treatment in real life settings[57,58]. By consolidating the full course of TMS treatments from weeks into days, aTMS offers advantages in addressing these challenges, making it particularly relevant for patients with addictive disorders. For example, in a conventional once-daily 20-session treatment course, patients need to visit the TMS clinic over 20 days. In contrast, this proposed accelerated protocol allows 20 sessions to be administered within 5 days, meaning patients only need to visit the clinic for 5 days. By further confirming the comparable effectiveness of accelerated TMS to the standard protocol, we expect this approach to greatly enhance the feasibility and acceptability of the treatment for patients.

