2.2 Secondary Objectives

Secondary Aim 1: To examine the effect of bilateral deep aTMS on short-term abstinence at the end of TMS treatment, at post-treatment follow-ups (point prevalence abstinence at Week 3, Week 5, Week 9, Week 13, Week 26),

Secondary Aim 2: To examine the effect of bilateral deep aTMS on prolonged and continuous abstinence at 3-month and 6-month follow-up (Week 13 and Week 26).

Secondary Aim 3: To examine the effect of bilateral deep aTMS on other smoking outcomes throughout study duration including self-reported craving, cigarette smoking and dependence severity.

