3.0 CLINICAL TRIAL DESIGN

3.1 Overall Design

This clinical trial is designed as a one-arm, open-label study to evaluate the efficacy and feasibility of the H4 deep accelerated transcranial magnetic stimulation (aTMS) protocol for smoking cessation. The absence of a control group is intentional, as this pilot study focuses on assessing the intervention's preliminary efficacy in a single arm of 40 participants with tobacco use disorder who are motivated to quit, aiming for 30 completers to guide a future controlled trial. Each participant's involvement will last 26 weeks, starting with a screening phase at Week 0, followed by a one-week treatment period in Week 1, and concluding with follow-up visits at Weeks 3, 5, 9, 13, and 26. The entire trial is expected to span approximately 2 years, covering recruitment, treatment, and follow-up for all participants.

During Week 1, participants will receive 20 rTMS sessions using the Health Canada-approved H4 deep TMS coil, administered at four sessions per day over five consecutive days, targeting the insular cortex, alongside brief counseling adapted from the Mayo Clinic's 'Smoke Free and Living It' manual. Daily assessments will monitor safety, Timeline Followback (TLFB), and nicotine craving and withdrawal symptoms. The primary outcome is overall feasibility, including measures of tolerability, acceptability, retention, and adherence. Secondary outcomes include 7-day point prevalence abstinence—verified by self-report and urine cotinine levels (<200 ng/mL)—at the end of treatment and at Weeks 3, 5, 9, 13, and 26. We will also assess 3-month abstinence at Week 13 and 6-month abstinence at Week 26, both verified by continuous self-reported abstinence during

the respective periods and corresponding urine cotinine levels. Factors such as comorbidities, pre-existing tobacco use disorder severity, or motivation level for abstinence may influence results; these are addressed through eligibility criteria and statistical adjustments.

It is anticipated that a proportion of enrolled participants may not proceed to the treatment phase (Week 1) due to scheduling, logistical, or personal factors. These individuals will be classified as early dropouts and excluded from the intent-to-treat analysis, which will include only participants who initiate at least one TMS session.

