4.3 Equity, Diversity and Inclusion Considerations

This study aims to recruit a diverse sample that reflects Ontario's population, ensuring the inclusion of historically underserved groups from various socioeconomic backgrounds. Given that we will also be recruiting participants at Sunnybrook Health Sciences Centre in Toronto, the most multicultural city in Canada, we anticipate strong minority group inclusion and will implement recruitment strategies that promote participation without restrictions based on race or ethnicity. Additionally, in alignment with Waypoint Centre for Mental Health Care's Equity, Diversity, and Inclusion strategy, we will integrate training on Indigenous Cultural Safety, Anti-Black Racism, and EDI principles to foster an inclusive research environment. Recruitment and retention strategies will also be designed to ensure that our research team and staffing reflect the diverse patient populations we serve.

Recognizing that sex and gender differences influence addiction and treatment outcomes, our study will integrate sex- and gender-based analysis to ensure a comprehensive approach to data interpretation. We will collect and analyze self-reported biological sex and gender identity to assess potential differences in treatment efficacy and interpret findings through a sex- and gender-based lens, ensuring that our recommendations remain relevant across diverse populations. Given established sex-related differences in smoking behaviors and nicotine metabolism, we will make every effort to recruit an equal number of male and female participants for robust sex-based analyses. Additionally, studies have shown that hormonal fluctuations can influence rTMS effects, with women exhibiting greater sensitivity to stimulation during periods of high estrogen. To ensure safety, pregnant or breastfeeding individuals will be excluded, as the safety of deep TMS in these populations has not been established.

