5.3 Method for Assigning Participants to Treatment Groups

Since this is a one-arm trial, all participants will receive accelerated deep TMS, with no randomization or allocation to different groups.

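### Sections 1.5 and 4.3 look to comparability with once-daily TMS and to efficacy by sex, neither of which one uncontrolled arm of 30 to 40 people can show

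*Protocol*

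**What the plan says.** **Comparability.** The Benefit part of Protocol 1.5 closes its argument for the shorter schedule with "By further confirming the comparable effectiveness of accelerated TMS to the standard protocol", and expects feasibility and acceptability to improve as a result.

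**Sex and gender.** Section 4.3 plans to use self-reported sex and gender to look for differences in how efficacious the treatment is, and adds: "we will make every effort to recruit an equal number of male and female participants for robust sex-based analyses".

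**Stated objective.** The Objectives row of the Clinical Trial Summary names efficacy on abstinence and does not mention feasibility. Section 2.1 makes feasibility the primary objective.

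**Design.** Section 5.3: "Since this is a one-arm trial, all participants will receive accelerated deep TMS, with no randomization or allocation to different groups". Section 3.1: "The absence of a control group is intentional", with the study "aiming for 30 completers to guide a future controlled trial". TMS is given "alongside brief counseling adapted from the Mayo Clinic's 'Smoke Free and Living It' manual". Section 6.1 schedules that counseling on days 1 and 5 of Week 1 and at Weeks 3, 5, 9, 13 and 26. Entry requires a Contemplation Ladder score of at least 7 (4.4.1), and treatment is timed to a target quit date (5.1).

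**Planning rates.** Section 7.1 cites 82.4% and 30.7% point-prevalence abstinence at Week 12 of an earlier trial, in which both arms took varenicline.

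**The concern.** Comparability and efficacy by subgroup are both contrasts. The first needs abstinence on once-daily TMS; the second needs untreated or sham abstinence within each sex. The protocol provides neither, and the rates in 7.1 do not fill the gap. They come with varenicline, whereas this trial excludes current users of cessation aids (4.4.2) and asks participants not to start cessation medication (5.6).

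What the trial will measure is abstinence after a package: accelerated TMS, counseling, a quit date and selection for motivation. If the protocol's wording carries over into the report, a reader could take an uncontrolled abstinence rate as evidence that the short schedule works as well as the long one, or that it works better in one sex. The pilot is meant to inform a controlled trial, so it should not appear to have answered that trial's question in advance.

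**Working it through.** **1. The plan's own figure.** Sections 3.1 and 7.1 give 40 enrolled for 30 completers. The implied loss is 1 − 30/40 = 25%, and 30/(1 − 0.25) = 40, so the inflation is consistent. No alpha, power, margin or precision target lies behind the 30, so it cannot be reproduced as a comparative sample size.

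**2. What one arm estimates.** At an assumed 50% abstinence, the 95% Wilson interval is 33.2% to 66.8% with n = 30 and 35.2% to 64.8% with n = 40. This describes the whole package.

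**3. Comparability.** The quantity needed is D = R(accelerated) − R(once daily). The second term has no data in this trial and no stated external value. D therefore has no estimate or interval, and there is no margin to judge it against.

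For scale only, take equal true rates p between 20% and 80%, one-sided alpha 0.025 and 80% power (all assumed). A two-arm non-inferiority comparison needs, per arm, n = (1.96 + 0.8416)² × 2p(1 − p)/margin²:

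| Margin (assumed) | n per arm |
|---|---|
| 10 points | 252 to 393 |
| 15 points | 112 to 175 |
| 20 points | 63 to 99 |

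The trial has 40 in one arm and none in the other. The fault is the missing arm; enlarging the single arm would not cure it.

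**4. Sex: what can be identified.** Write each sex's abstinence as a background rate b (counseling, motivation, quit date) plus a TMS contribution t. Then

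R(male) − R(female) = [b(male) − b(female)] + [t(male) − t(female)].

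Only the left side is observed. A gap may be entirely background, and a zero gap may hide a real difference in t. Section 4.3 itself refers to known sex differences in smoking behavior and nicotine metabolism, so b cannot be assumed equal.

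**5. Sex: precision.** With an equal split, 30 completers give 15 per sex and 40 enrolled give 20 per sex. The half-width is 1.96 × √(2p(1 − p)/n), with p assumed:

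| p | 15 per sex | 20 per sex |
|---|---|---|
| 50% | 1.96 × √(0.50/15) = 1.96 × 0.183 = 36 points | 1.96 × √(0.50/20) = 1.96 × 0.158 = 31 points |
| 20% or 80% | 1.96 × √(0.32/15) = 1.96 × 0.146 = 29 points | 1.96 × √(0.32/20) = 1.96 × 0.126 = 25 points |

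Power for a true 20-point gap at 15 per sex (two-sided 5%, assumed) is Φ[(d − 1.96·SE0)/SE1], where SE0 uses the pooled rate and SE1 the two separate rates. For 20% vs 40%, SE0 = √(2 × 0.30 × 0.70/15) = 0.167 and SE1 = √((0.16 + 0.24)/15) = 0.163, which gives about 22%. For 30% vs 50% the result is about 20%.

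**The case against.** The strongest reply is that the protocol already presents itself as a pilot. The primary objective is feasibility (2.1). Section 3.1 says the lack of a control is deliberate, calls efficacy preliminary and openly describes the counseling. Section 7.1 calls the work exploratory. The comparability clause is rationale text and could express a goal of the wider research programme. No objective, endpoint or analysis in the protocol carries out a comparison with once-daily TMS. All of this stands, and it limits the point to wording. It does not supply a comparator for what 1.5 and 4.3 say.

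A reader might infer more than the document supports, in three ways:

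- **That Aims 1-3 claim a proven causal effect.** Section 2.2 says "To examine the effect of bilateral deep aTMS on short-term abstinence at the end of TMS treatment", which is ordinary phrasing for a pilot aim. Section 3.3 turns it into proportions abstinent and changes from baseline.
- **That the trial undertakes to isolate the accelerated schedule.** The remark in 1.4 that "isolating the effect of the accelerated treatment schedule is crucial to understand this technique" follows a discussion of depression studies and states a need of the field. It is not a claim about this trial.
- **That following the analysis plan would produce a finding of comparability or of efficacy by sex.** The model in 7.2 has time as a fixed effect and subject as a random intercept, with a few baseline covariates. It names no once-daily contrast and no sex contrast. Only 1.5 uses a confirmatory verb; 4.3 speaks of potential differences.

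On precision, 50% abstinence is the widest case. Completers are also not the planned denominator, since 3.1 and 7.2 analyse everyone with at least one session. Both points are fair, which is why the range is shown. Intervals of 25 to 36 points either side still do not justify calling the analyses robust. Section 7.2 promises 95% intervals, so the imprecision would be visible in the report.

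**Conclusion.** The point holds for three pieces of text: the comparability clause in 1.5, the sex-based efficacy language in 4.3, and the efficacy objective in the Clinical Trial Summary. A single uncontrolled arm cannot support the first two. The third does not match the feasibility objective in 2.1.

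For comparability the shortfall is complete, as no estimate is possible. For sex, the contrast does not identify efficacy. Even as a plain difference in abstinence it carries about ±31 points at 20 per sex or ±36 at 15 per sex, assuming an equal split and 50% abstinence, and ±25 to ±29 if abstinence is 20% or 80%. The conclusion on identification does not depend on these assumed rates.

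This is a fault in what the protocol says it will learn. The choice of a single-arm feasibility pilot is not in question.

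**What to change.** 1. In 1.5, delete the clause on comparable effectiveness and state that comparison with once-daily TMS is left to the future controlled trial.
2. In 4.3, drop the word robust and the reference to treatment efficacy. Say that abstinence will be reported by sex and gender descriptively, with 95% intervals.
3. In the Clinical Trial Summary, align the objective with 2.1 by putting feasibility first. Describe abstinence as the within-arm rate after accelerated deep TMS given with brief counseling in smokers motivated to quit.
4. Optional: use the same description in Aims 1-3 of 2.2.

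The cost is a protocol text amendment and a more modest stated claim. Procedures, sample size, data collection and the model in 7.2 stay as they are.
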